4 DATABASE LOCK

The database is planned to be locked when all patients have completed at least 4 postbaseline tumor assessments, experienced confirmed objective response, or discontinued the study for any reason.

In case of early discontinuation of the study (for futility for instance), the database lock can be performed when all patients have completed at least 2 postbaseline tumor assessments, experienced confirmed objective response, or discontinued the study for any reason.

5 SOFTWARE DOCUMENTATION

All summaries and statistical analyses will be generated using SAS version 9.4 or higher.

7 LIST OF APPENDICES

- [Appendix A](#): Specification of the Bayesian design in Part 1
- [Appendix B](#): Determination of tumor response
- [Appendix C](#): Modified Response Evaluation Criteria in Solid Tumors (RECIST 1.1)
- [Appendix D](#): SOC internationally agreed order
- [Appendix E](#): Potentially clinically significant abnormalities criteria for vital signs
- [Appendix F](#): Description of primary and sensitivity analyses of PFS
- [Appendix G](#): Generic ranges for hematological and biochemistry parameters

Appendix A Specification of the Bayesian design in Part 1

Primary objective of the study:

Objectives of the study are to select the dose based on overall response rate and safety of 2 dose levels 90 mg/m² D1D8 Q3w and 120 mg/m² D1D8 Q3w.

During the part 1 of the study, 14 patients will be included in both dose levels.

Safety will be monitored and the risks for predefined safety criteria (PSC) during the first 2 cycles will be followed for patients in part 1 of the study. We will use a Bayesian binomial model as a monitoring tool.

Following predefined safety criteria have been selected for the study:

- Grade ≥ 3 TEAE from SOC eye disorders
- Grade ≥ 3 TEAE peripheral neuropathy (Preferred Term)
- Grade ≥ 4 TEAE

PSC evaluation will be performed on patients treated in the study who have completed 2 cycles, or who experienced predefined safety criteria (whatever the dose received).

The design will recommend a GO decision if it verifies overdosing risk constraints in the population:

- No more than 0.25 risk to recommend an overdosing dose (true PSC rate above 0.40).
- No more than 0.05 risk to recommend an unacceptable toxicity dose (true PSC rate above 0.60).

And so we will recommend to stop a dose level when overdosing dose or unacceptable toxicity are not controlled at the specific levels.

The Bayesian model is planned to be run after 4 evaluable patients at dose level 120 mg/m² D1D8Q3W.

The calculation will be done independently for the two tested doses 90 mg/m² D1D8Q3w and 120 mg/m² D1D8Q3W.

Assumptions for prior elicitation

Prior distribution is elicited using the data from the first in human study (TED10499).

As dose level 90 mg/m² D1D8 Q3w has been already given in the phase I study, these data will be taken into account for the prior distribution of this dose level.

Dose level 120 mg/m² D1D8 Q3w has never been tested before. As preliminary PK/PD analyses show that the dose intensity (mg/m²/week) is predictive of the occurrence of ocular toxicity (one of the predefined safety criteria), the data from dose level 240 mg/m² Q3w with same dose intensity will be used for the elicitation of the prior distribution for the dose level 120 mg/m² D1D8 Q3w.

Table 4 provides the final results for both dose level selected from the phase I as prior distribution of the Bayesian model:

Table 4 - Results from the phase I TED10499 study

Dose Levels and schedules	90 mg/m ² D1D8 Q3w	240 mg/m ² Q3w
Number of patients	17	8
Number of PSC	1	2

Data from phase I are less informative than from phase II. Indeed patients selected for phase II are only CA6 positive with metastatic Triple Negative Breast Cancer and also they will all receive primary prophylaxis during their treatment whereas only some patients received primary prophylaxis during the phase I.

That is why a discount parameter k and k' is added for the corresponding dose level 90 mg/m² D1D8 Q3w and 120 mg/m² D1D8 Q3w such as:

$$0 < k' < k \leq 1$$

and so 1 patient from the phase II will correspond to k or k' patients from the phase I. k' will also be lower than k , since prior information for dose level 120 mg/m² D1D8 Q3w are not coming from the exact same dose level.

Table 5 provides the information from phase I including discount parameter:

Table 5 - Results from the phase I TED10499 study including discount parameter

Dose Levels and schedules	90 mg/m ² D1D8 Q3w	240 mg/m ² Q3w
Number of patients	17k	8k'
Number of PSC	1k	2k'

There is no information before the phase I study, so the minimally informative beta distribution will be used. It will be the Jeffrey's prior beta distribution Beta (0.5, 0.5).

Resulting beta distributions after phase I:

- Beta(0.5+1k, 0.5+17k-1k) for dose level 90 mg/m² D1D8Q3w
- Beta(0.5+2k', 0.5+8k'-2k') for dose level 120 mg/m² D1D8Q3w

Posterior distribution

The posterior distributions after n (or n') additional patients and x (or x') PSC respectively for dose level 90 mg/ m² D1D8Q3w (or 120 mg/m² D1D8Q3w) become

- Beta(0.5+1k+x, 0.5+17k-1k+n-x) for dose level 90 mg/m² D1D8Q3w
- Beta(0.5+2k'+x', 0.5+8k'-2k'+n'-x') for dose level 120 mg/m² D1D8Q3w

Risk of overdosing and unacceptable toxic dose

If we note the previous distributions Beta(a,b), p-values for overdosing and unacceptable toxicity are derived for each dose following the formulas as below:

$$p_{\text{overdosing}} = 1 - F_{\text{beta}}(\text{threshold}_{\text{overdosing}}, a, b)$$
$$p_{\text{unacceptable toxicity}} = 1 - F_{\text{beta}}(\text{threshold}_{\text{unacceptable toxicity}}, a, b)$$

with F_{beta} the distribution function of Beta(a,b).

Choice for k and k'

Based on rules already defined above for k and k', some simulations have been run to find a value for k and k'. The target was to find a k and k' which will minimize the probability to take a wrong decision in any cases whatever the number of PSC found when we will run the Bayesian model at 4 or 8 patients (which are numbers of patients where we planned to use the Bayesian model). And in the same time, we would like k and k' which allow us to give some weight to the phase I and phase II in order for both results to be a part of the Go/No Go decisions.

For simulations, we will:

- Run the Bayesian model for 4 or 8 patients and see what will be the decision when 0, 1, 2, 3 or 4 PSC(s) occur(s).
- Using phase I result and for each case, a probability of PSC have been generated to simulate the rest of the patient until to get 14 patients for the phase II.
- 1000 simulations have been generated in order to calculate the probability of wrong decision where we compare the first decision at 4 or 8 patients with the simulated decision at 14 patients (do the decision will be the same at 4 or 8 patients compare to the decision taken with simulated data at 14 patients).

So simulations will be performed for each k and k' from 0.1 to 0.9 and following tables and figures show the results for probability of wrong decision for k and k' when we run the Bayesian model at 4 and 8 patients:

Figure 2 - Graph of probability of wrong decision by k values –90 mg/m² D1D8 Q3w at 4 patients

[figure not shown]

Figure 3 - Graph of probability of wrong decision by k values – 90 mg/m2 D1D8 Q3w at 8 patients

[figure not shown]

Table 6 - Probability of wrong decision by k values – 90 mg/m² D1D8 Q3w at 4 and 8 patients

Probability of wrong decisions by k values - Dose level 90 mg/m ² D1D8 Q3w at 4 patients									
PSC	k								
	0,1	0,2	0,3	0,4	0,5	0,6	0,7	0,8	0,9
0	0,028	0,01	0,005	0,001	0	0	0	0	0
1	0,276	0,096	0,061	0,012	0,012	0,001	0,001	0	0
2	0,335	0,588	0,331	0,125	0,091	0,028	0,021	0,002	0
3	0,05	0,216	0,325	0,57	0,363	0,152	0,115	0,034	0,006
4	0,004	0,028	0,06	0,228	0,314	0,554	0,388	0,174	0,057
Sum1	0,693	0,938	0,782	0,936	0,78	0,735	0,525	0,21	0,063
Probability of wrong decisions by k values - Dose level 90 mg/m ² D1D8 Q3w at 8 patients									
PSC	k								
	0,1	0,2	0,3	0,4	0,5	0,6	0,7	0,8	0,9
0	0,001	0	0	0	0	0	0	0	0
1	0,015	0,001	0,001	0	0	0	0	0	0
2	0,204	0,046	0,031	0,004	0,001	0	0	0	0
3	0,411	0,292	0,236	0,055	0,047	0,004	0,001	0	0
4	0,07	0,334	0,395	0,304	0,26	0,066	0,057	0,006	0
5	0	0,048	0,07	0,331	0,386	0,312	0,273	0,075	0,016
6	0	0	0	0,052	0,068	0,334	0,368	0,318	0,098
7	0	0	0	0	0	0,057	0,073	0,334	0,63
8	0	0	0	0	0	0	0	0,06	0,302
Sum2	0,701	0,721	0,733	0,746	0,762	0,773	0,772	0,793	1,046
Sum1+Sum2	1,394	1,659	1,515	1,682	1,542	1,508	1,297	1,003	1,109

As a higher k will give a weight too important to the phase I study and not enough weight to the phase II, we choose k=0.3 for dose level 90 mg/m² D1D8 Q3w since this is the best intermediate value which minimizes the probability of wrong decision whatever the number of PSC that appear at 4 or 8 patients.

Same work has been done for the dose level 120 mg/m² D1D8 Q3w.

Figure 4 - Graph of probability of wrong decision by k' values – 120 mg/m² D1D8 Q3w at 4 patients

[figure not shown]

Figure 5 - Graph of probability of wrong decision by k' values – 120 mg/m2 D1D8 Q3w at 8 patients

[figure not shown]

Table 7 - Probability of wrong decision by k' values –120 mg/m² D1D8 Q3w at 4 and 8 patients

Probability of wrong decisions by k values - Dose level 120 mg/m ² D1D8 Q3w at 4 patients									
PSC	k'								
	0,1	0,2	0,3	0,4	0,5	0,6	0,7	0,8	0,9
0	0,042	0,055	0,063	0,057	0,057	0,056	0,06	0,024	0,022
1	0,643	0,356	0,345	0,336	0,329	0,33	0,321	0,171	0,169
2	0,216	0,25	0,265	0,287	0,304	0,321	0,336	0,516	0,527
3	0,017	0,026	0,037	0,046	0,055	0,059	0,064	0,185	0,196
4	0	0,002	0,003	0,003	0,003	0,004	0,004	0,026	0,031
Sum1	0,918	0,689	0,713	0,729	0,748	0,77	0,785	0,922	0,945
Probability of wrong decisions by k values - Dose level 120 mg/m ² D1D8 Q3w at 8 patients									
PSC	k'								
	0,1	0,2	0,3	0,4	0,5	0,6	0,7	0,8	0,9
0	0,001	0,001	0,002	0	0,001	0,001	0,001	0	0
1	0,024	0,024	0,029	0,027	0,026	0,025	0,033	0,006	0,005
2	0,252	0,247	0,244	0,239	0,236	0,232	0,23	0,067	0,067
3	0,359	0,368	0,375	0,379	0,387	0,393	0,4	0,663	0,666
4	0,042	0,049	0,056	0,064	0,065	0,068	0,07	0,309	0,313
5	0	0	0	0	0	0	0	0,046	0,051
6	0	0	0	0	0	0	0	0	0
7	0	0	0	0	0	0	0	0	0
8	0	0	0	0	0	0	0	0	0
Sum2	0,678	0,689	0,706	0,709	0,715	0,719	0,734	1,091	1,102
Sum1+Sum2	1,596	1,378	1,419	1,438	1,463	1,489	1,519	2,013	2,047

For dose level 120 mg/m² D1D8 Q3w, k'=0.2 give the lowest probability of wrong decision, so it will be choose for this dose level.

Results of the Bayesian model:

As we decide to use k=0.3 for dose level 90 mg/m² D1D8 Q3w and k'=0.2 for dose level 120 mg/m² D1D8 Q3w, we can run the Bayesian model for 3, 4, 6 and 8 patients and see what will be the decision when 0, 1, 2, 3 or 4 toxicity occurs.

As we did previously, we will do simulations in order to calculate two probabilities of wrong decision:

Compare to simulated decision at 14 patients: do the decision will be the same at 3, 4, 6 or 8 patients compare to the decision taken with simulated data at 14 patients.

Compare to the probability of toxicity generated using phase I results and data at 3, 4, 6 or 8 patients: do the decision taken after 3, 4, 6 and 8 patients is in agreement with the probability of toxicity.

Table 8 - Bayesian decision – 90 mg/m² D1D8 Q3w at 3 patients

Analysis at 3 patients at 90mg/m ² Q3W D1D8					
Number of PSC	Decision	Overdosing probability	Unacceptable probability	Probability of wrong decision	
				Compare to simulated decision at 14 patients (1)	Compare to the probability of toxicity (2)
0	GO	0,94%	0,03%	1,4%	0,7%
1	GO	7,61%	0,51%	11,3%	7,5%
2	No GO	25,64%	3,42%	56,7%	74,9%
3	No GO	52,69%	13,23%	20,6%	48,4%

Table 9 - Bayesian decision – 90 mg/m² D1D8 Q3w at 4 patients

Analysis at 4 patients at 90mg/m ² Q3W D1D8					
Number of PSC	Decision	Overdosing probability	Unacceptable probability	Probability of wrong decision	
				Compare to simulated decision at 14 patients (1)	Compare to the probability of toxicity (2)
0	GO	0,55%	0,01%	0,5%	0,2%
1	GO	4,94%	0,22%	6%	4,7%
2	GO	18,43%	1,67%	33%	17,2%
3	No GO	41,87%	7,34%	32,7%	58,8%
4	No GO	67,79%	21,45%	6,1%	32,5%

Table 10 - Bayesian decision – 90 mg/m² D1D8 Q3w at 6 patients

Analysis at 6 patients at 90mg/m2 Q3W D1D8					
Number of PSC	Decision	Overdosing probability	Unacceptable probability	Probability of wrong decision	
				Compare to simulated decision at 14 patients (1)	Compare to the probability of toxicity (2)
0	GO	0,19%	0%	0,1%	0,1%
1	GO	2,04%	0,04%	1%	2,1%
2	GO	9,09%	0,38%	13,3%	7,7%
3	GO	24,71%	2,06%	46,1%	24,4%
4	No GO	47,45%	7,56%	18,7%	52,5%

Table 11 - Bayesian decision – 90 mg/m² D1D8 Q3w at 8 patients

Analysis at 8 patients at 90mg/m2 Q3W D1D8					
Number of PSC	Decision	Overdosing probability	Unacceptable probability	Probability of wrong decision	
				Compare to simulated decision at 14 patients (1)	Compare to the probability of toxicity (2)
0	GO	0,07%	0%	0%	0,12%
1	GO	0,83%	0,01%	0,24%	0,74%
2	GO	4,28%	0,08%	3,82%	4,36%
3	GO	13,59%	0,53%	23,22%	13,04%
4	No GO	30,4%	2,33%	36,98%	69,74%

Table 12 - Bayesian decision – 120 mg/m² D1D8 Q3w at 3 patients

Analysis at 3 patients at 120mg/m2 Q3W D1D8					
Number of PSC	Decision	Overdosing probability	Unacceptable probability	Probability of wrong decision	
				Compare to simulated decision at 14 patients (1)	Compare to the probability of toxicity (2)
0	GO	7,72%	1,11%	9,6%	6,8%
1	No GO	35,18%	9,94%	50,9%	65,6%
2	No GO	70,84%	35,72%	12,3%	29,3%
3	No GO	92,97%	71,72%	1%	5,3%

Table 13 - Bayesian decision – 120 mg/m² D1D8 Q3w at 4 patients

Analysis at 4 patients at 120mg/m2 Q3W D1D8					
Number of PSC	Decision	Overdosing probability	Unacceptable probability	Probability of wrong decision	
				Compare to simulated decision at 14 patients (1)	Compare to the probability of toxicity (2)
0	GO	4,56%	0,44%	5,4%	4,2%
1	GO	24,2%	4,64%	35,3%	24,1%
2	No GO	56,58%	20,25%	25,3%	43,9%
3	No GO	84,12%	50,12%	2,7%	14,4%
4	No GO	96,83%	81,14%	0,2%	3,1%

Table 14 - Bayesian decision – 120 mg/m² D1D8 Q3w at 6 patients

Analysis at 6 patients at 120mg/m ² Q3W D1D8					
Number of PSC	Decision	Overdosing probability	Unacceptable probability	Probability of wrong decision	
				Compare to simulated decision at 14 patients (1)	Compare to the probability of toxicity (2)
0	GO	1,6%	0,07%	1,1%	1,2%
1	GO	10,89%	0,95%	13,7%	10,1%
2	No GO	32,71%	5,63%	50,6%	68,7%
3	No GO	61,31%	19,41%	13,9%	38,9%
4	No GO	84,29%	44,33%	1%	14,5%

Table 15 - Bayesian decision – 120 mg/m² D1D8 Q3w at 8 patients

Analysis at 8 patients at 120mg/m ² Q3W D1D8					
Number of PSC	Decision	Overdosing probability	Unacceptable probability	Probability of wrong decision	
				Compare to simulated decision at 14 patients (1)	Compare to the probability of toxicity (2)
0	GO	0,57%	0,01%	0,22%	0,48%
1	GO	4,69%	0,19%	3,48%	4,36%
2	GO	17,26%	1,38%	24,06%	16,78%
3	No GO	39,52%	6,15%	33,9%	60,7%
4	No GO	65,01%	18,44%	5,04%	34,92%

Appendix B Determination of tumor response

The overall response at each time point and the best overall response will be determined by the Investigator derived from the tumor measurements data according to RECIST 1.1 criteria ([Appendix C](#)) using the following algorithm.

- Overall Response:

Overall response, or integrated response, will be determined by the investigator using assessments of target, non-target and new lesions according to RECIST 1.1. See [Appendix C](#) for details.

- Confirmation:

According to RECIST 1.1 a confirmed CR or PR will be based on two tumor assessments at least four weeks apart as follows: if a CR or PR outcome is reported, then a second tumor assessment with CR or PR at least four weeks later is needed for confirmation, regardless of how many “unknown/not applicable/missing/non evaluable” tumor assessments are in between the two outcomes.

- Best Overall Response (BOR) :

In general, a patient’s best tumor response will depend on the achievement of both: documented tumor measurement assessments and confirmation of the tumor response by RECIST1.1 criteria. For each patient the BOR will be derived based on the following algorithm:

– a) PR/CR will be determined based on confirmed PR and confirmed CR described in the algorithm above.

– b) SD and PD will be determined from the overall tumor response at each timepoint. If SD is the overall response and it occurs less than 35 days from first study administration, then overall response will not be SD. For patients who stop the treatment due to a symptomatic deterioration or death, without any other tumor assessment before the symptomatic deterioration or death, then the BOR will be considered as NE. These cases will be described separately as patients in early progression or early death.

If PD is the overall response and it occurs less than 42 days from the first study administration, then the best overall response is PD.

– c) Convention for PD after several NE cycles: in the case where the assessment at study entry is followed by several visits (or cycles) with no assessment (or only NE assessments or SD <35 days from first study administration) for more than twice the periodicity of tumor assessments (ie, for more than 42 days), and the next assessment is PD, the best overall response will be NE. If the PD occurs within this period of time, the best overall response will be PD.

Using the outcome from a), b) and c) above, the BOR will be determined based on the following order of Overall Responses: CR, PR, SD, PD and NE.

In the BOR determination, tumor assessments performed after a patient started post-treatment anti-tumor therapy will not be considered. The date of post-treatment anti-tumor therapy for a patient will be the earliest date among the dates for “Post Treatment Anti-Cancer Drug Therapy”, “Post Treatment Radiation Therapy” and “Post-Treatment Anti-Cancer Surgery” for target and non-target lesions identified at baseline. Assessments performed after the earliest post-treatment anti-tumor therapy will be excluded from the determination of BOR. If, in the same tumor evaluation period, several assessments are performed before the first post-treatment anticancer therapy and several assessments are performed afterwards, the disease assessment will be included in the determination of BOR.

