- **Blood sampling for PK:** as specified in PK/immunogenicity flow chart (see [Section 1.4](#)).
- **Blood sampling for ATA:** as specified in PK/immunogenicity flow chart (see [Section 1.4](#)).
- **Tumor assessment** every 6 weeks after first study treatment administration: (abdominal/chest) CT Scan or MRI, and all other exams as clinically indicated (eg, brain CT scan or MRI in case of clinical suspicion of central nervous system involvement) to assess all TARGET or NON TARGET lesions. To ensure comparability, the imaging should be performed using identical techniques throughout the study period (ie, scans performed immediately following bolus contrast administration using a standard volume of contrast, the identical contrast agent, and preferably the same scanner).

Confirmation of objective responses will be performed by repeat tumor imaging (CT scan, MRI) at least 4 weeks after the first radiological documentation of response (see [Section 9.1.2](#)).
- **Other investigations** if clinically indicated.

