2.1.3 Efficacy endpoints

2.1.3.1 Primary efficacy endpoint(s)

The primary efficacy endpoint will be the Overall Response Rate (ORR) defined as the proportion of patients with confirmed complete response (CR) or confirmed partial response (PR) as Best

Overall Response (BOR), assessed by the Investigator (based on RECIST 1.1), relative to the total number of patients in the efficacy population (see [Section 2.3.1](#)). Confirmation of objective responses will be performed by repeat tumor imaging (Computed Tomography [CT] scan, MRI) at least 4 weeks after the first radiological documentation of response.

Tumor assessments will be performed every 6 weeks (ie, every 2 cycles) during the treatment period and every 6 weeks during the follow-up period if a patient discontinues treatment prior to radiologic disease progression.

Tumor assessments after the initiation of post-treatment anti-cancer therapy will be excluded from the determination of Best Overall Response in a patient. See [Appendix B](#) (Determination of tumor response) for details.

Best Overall Response

BOR is the best tumor response observed from first study treatment infusion until disease progression, death or initiation of post-treatment anti-cancer therapy, whichever occurs first.

Primary ORR analysis can be performed when all patients treated in Part 2a and Part 2b have had at least 4 postbaseline tumor assessments, experienced confirmed objective response, or have discontinued the study for any reason. However, if the primary criteria of 7 responders is either met or not met with certainty at the end of the Part 2a in the selected dose when all patients have had 2 postbaseline tumor assessments, experienced confirmed objective response, or discontinued the study for any reason and when all the patients of the Part 2b have had 2 postbaseline tumor assessments, experienced confirmed objective response, or discontinued the study for any reason, analysis may be done at that time instead.

Best tumor shrinkage

For patients with measurable disease, the best tumor shrinkage will be defined by the best relative change from baseline as follows:

$$Y = 100 \times \frac{Y_{smallest} - Y_{baseline}}{Y_{baseline}}$$

Where Y is the sum of longest diameter of the target lesions.

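### SAP Appendix B item c equates twice the scan interval with 42 days when it is 84, so progression on a slightly late week-6 scan can be tabulated as not evaluable

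*SAP*

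**What the plan says.** Protocol 10.1.4 schedules on-treatment scans "every 6 weeks after first study treatment administration". SAP 2.1.3.1 agrees: "Tumor assessments will be performed every 6 weeks (ie, every 2 cycles) during the treatment period".

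SAP Appendix B derives BOR in three items, a to c, and then ranks the results.

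- **Item b** deals with early progression: "If PD is the overall response and it occurs less than 42 days from the first study administration", BOR is PD.
- **Item c** applies where "the assessment at study entry is followed by several visits (or cycles) with no assessment". Assessments that are all NE, or SD before day 35, are treated in the same way. If this lasts "for more than twice the periodicity of tumor assessments (ie, for more than 42 days), and the next assessment is PD", BOR is NE. Its closing sentence covers the other case: "If the PD occurs within this period of time, the best overall response will be PD".
- **Ranking:** from the outcomes of a, b and c, "the BOR will be determined based on the following order of Overall Responses: CR, PR, SD, PD and NE".

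SAP 2.4.4.1 plans a BOR table with PD and NE as separate categories. SAP 2.3.1 repeats BOR as a sensitivity analysis on the response evaluable population.

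**The concern.** Item c gives its limit twice, once in words and once in days, and the two differ by a factor of two. The limit decides whether a documented progression is reported as PD or as NE, so it is an operative derivation rule.

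If the number is programmed, a patient whose week-6 scan is a few days late and shows progression can be classed as not evaluable. That patient has skipped nothing. The same scan would still be a PFS event under SAP Appendix F, Table 20, and an evaluable, non-NE assessment under SAP 2.3.1.2.

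If the words are programmed, the patient is PD. Two programmers working from the same text could therefore produce different BOR tables.

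**Working it through.** **Inputs**

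- Scan interval: 6 weeks (Protocol 10.1.4; SAP 2.1.3.1).
- Cycle length: 21 days.
- Limit in item c: twice the scan interval in words, 42 in days.
- Treatment period: last infusion + 30 days (SAP 2.1.4).
- Denominators: 14 per Part 1 dose arm, 29 in the overexpression cohort at the selected dose, 20 in Part 2b.

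**Step 1. Try to reproduce the 42 days.**

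- Interval = 6 × 7 = 42 days.
- Twice the interval = 2 × 42 = 84 days.

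The stated 42 is not reproduced as twice the interval. It equals one interval, and also two cycles (2 × 21 = 42), but item c refers to tumor assessments.

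**Step 2. Apply both limits to a patient whose first usable assessment is PD, counting from first dose.**

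| Day of the PD scan | Limit 42 | Limit 84 |
|---|---|---|
| up to 42 | PD | PD |
| 43, 45, 49, 56, 63, 84 | NE | PD |
| 85 | NE | NE |

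The readings differ on days 43 to 84. The practical concern is the lower end of that range, because a scan near day 84 is the week-12 scan. The documents give no window for on-treatment scans. Borrowing the ±1 week that Protocol 10.1.6 allows for follow-up visits gives 42 + 7 = 49, so days 43 to 49 serve as the illustration. If a site ties scans to cycles, the 2-week treatment delay permitted by Protocol 8.2.3.2 could move the scan to 42 + 14 = day 56.

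**Step 3. Check whether the trigger spares such a patient.** Two 21-day cycles pass before any on-schedule first scan. A patient scanned on time and one scanned a few days late have the same run of cycles without an assessment, and the text does not say how many cycles or visits count as several. The day limit is what separates them.

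**Step 4. Check the starting point.** Item c starts from the study-entry assessment and does not say where the day count begins. Item b and SAP 2.1.3.1 count from first dose ("BOR is the best tumor response observed from first study treatment infusion until disease progression"). Protocol 9.1.2 allows the baseline scan up to 21 days before first dose. Counted from that scan, an on-time week-6 scan falls 42 to 63 days later (0 + 42 to 21 + 42). Even an on-time PD could then exceed 42 days, though never 84.

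**Step 5. Check that the scan is otherwise evaluable.** With Cycle 2 started on time, the treatment period ends at day 21 + 30 = 51 if the last infusion was Cycle 2 Day 1, or at day 28 + 30 = 58 if it was Cycle 2 Day 8. A PD scan on days 43 to 49 lies inside both, so it is an evaluable assessment under SAP 2.3.1.2.

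**Step 6. Size per affected patient.** 1/14 = 7.1 points, 1/29 = 3.4 points and 1/20 = 5.0 points, moved from PD to NE.

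**Step 7. What does not move.** PD and NE are both non-responses, and SAP 2.5.3 keeps non-evaluable patients in the denominator as non-events. ORR and its interval, the 2/14, 6/14 and 7/29 rules, and DCR are therefore unchanged. PFS and TTP use the documented progression itself and are also unchanged.

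**The case against.** The strongest reply is that item c was never meant for a late first scan. Its heading concerns PD after a run of NE cycles, and a patient scanned a few days late has no NE cycle. Item b takes PD from the response at each timepoint, and the final ranking puts PD above NE. On that view the patient is PD whichever number is printed.

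Part of this stands: NE is the literal result of the printed number and not a certain one. But the body of item c goes beyond its heading and also covers visits or cycles with no assessment at all. The ranking works on the outcome of item c, which has already assigned NE. If the ranking always restored PD, item c would have no effect.

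A second reply is that the word may be wrong and the number right. Item b also uses 42 days, and 42 days is two cycles. The documents do not settle this, so the fix below covers both possibilities. SAP 2.5.5 tabulates tumor assessments by recorded cycle, but it concerns by-cycle summaries and does not define BOR.

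A third reply is that a scan can be a PFS event while BOR is NE at any cut-off, including after day 84. That is correct. The 84-day limit removes the conflict for days 43 to 84 only.

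Finally, the effect on the trial's conclusions is nil and the number of affected patients may be zero. This is accepted, and it is why the point is minor.

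**Conclusion.** The concern holds, as a minor point. Item c contradicts itself: its wording gives 84 days and its number gives 42. The contradiction can change BOR between PD and NE when the first usable assessment is PD on days 43 to 84. The realistic case is a week-6 scan that is modestly late.

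Each such patient moves 3.4 to 7.1 points between two categories of the BOR table, depending on the cohort. No responder count, decision rule or time-to-event analysis is affected.

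The arithmetic is certain. The NE outcome assumes that the printed number is programmed, that two cycles without a scan meet the trigger, and that item c's result is not overridden by the ranking. The 43-to-49-day illustration also assumes counting from first dose and a tolerance borrowed from the follow-up visits.

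**What to change.** In SAP Appendix B item c, replace 42 with 84 days so that the number matches the wording, and state that the count runs from first dose, as in item b and SAP 2.1.3.1. The closing sentence of item c then gives PD for a late first scan, and item b needs no new clause.

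If one interval was intended, delete the word twice instead, and state how many days late the first scan may be before PD becomes NE.

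Either way the cost is a small text change before database lock, with no effect on data collection or design.
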